2.3 Statistical Methods

2.3.1 Demography and baseline characteristics

Demographic information will be statistically summarized by treatment group.

2.3.2 Analysis of Feasibility

This will be the percentage of individuals who consented to be a part of the study out of the total number of approached individuals.

2.3.3 Analysis of Acceptability

Exit interviews were aucio recorded, transcribed, and qualitatively content analyzed in a deductive maner to provide context on acceptability.

2.3.4 Analysis of Satisfaction

The mean score will be summarized by treatment group and survey time point.

The difference between the mean values at each time point will be calculated by treatment group. Differences in these change values by group will be examined using sample t-tests.

2.3.5 Analysis of Efficacy

Mean values of the efficacy outcomes will be summarized by treatment group and survey time point.

The difference between the mean values at each time point will be calculated by treatment group. Differences in these change values by group will be examined using sample t-tests.

Multivariable linear regression models will be run for each efficacy outcome. We will control for facility, age at diagnosis, insurance type at diagnosis and gender while examining if treatment group is significantly different in the models.

We will run multivariable linear models stratified by age at diagnosis and insurance type to examine possible confounding.

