1.1 Study Design & Randomization

This is a multi-site behavioral intervention study. The study will be run between August 2020 and December 2021. For randomization, participants will be stratified by age at cancer diagnosis (17-26; 27-39 years) and treatment site and blocked into groups of 4 patients (2 control, 2 intervention) to ensure that control and intervention groups are approximately balanced by age and within sites. Random allocations within strata will be computer generated and automatically assign individuals to a study arm after the study coordinator determines patients' eligibility and obtains consent. All participants will then take a baseline survey and meet with the patient navigator. Participants enrolled in the intervention group will attend 4 educational sessions to learn about health insurance. Participants not enrolled in the intervention group will have access to the patient navigator for assistance, as is standard care. Participants will all take a follow-up survey. A randomly selected group of all participants will be interviewed after the follow-up survey.

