1.3 Study Outcomes

Primary Outcome:

Feasibility

The percent of AYA cancer patients enrolled in the study will be used as the measure of feasibility.

Acceptability

Information on acceptability of the program material and the Zoom format and what they liked or disliked about the intervention content

Satisfaction

Satisfaction with the Interpersonal Relationship with the Navigator score (PSN-I)¹⁻² will be used as the measure of acceptability. This consists of the sum of 9 items with a higher score indicating greater participant satisfaction with the relationship between themselves and the navigator. Participants will be asked these questions during the follow-up survey.

Secondary Outcome:

Efficacy

Differences in baseline and follow up response values for health insurance literacy and financial toxicity will be used to measure efficacy.

Health insurance literacy will be measured using two sections of the Health Insurance Literacy Measure (HILM)³ as well as questions concerning familiarity with provisions of the affordable care act, and laws surrounding insurance (e.g. COBRA, ADA). The sum of responses from each of these categories of questions will be used where higher scores indicate higher literacy.

Financial toxicity will be measured using the COmprehensive Score for financial Toxicity (COST)⁴. The COST score consists of 11 questions where lower scores indicate higher financial toxicity.

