1.4 Sample Size Calculation

Sample size was calculated using the two mean sample test in STATA 14. The study should have at least 80% power to detect differences in the mean improvement in the COST score between the intervention and control groups which differ by 0.67 SD based for our target of N=72 completion.

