2.1.2 Efficacy

Our efficacy measures will be collected at both baseline and follow-up as this study is interested in examining the change between the two timepoints. These measures include 9 items on confidence using and being proactive with insurance selected from the Health Insurance Literacy Measure (HILM) and 7 items on familiarity with insurance protections under the Affordable Care Act (ACA). For each of these measures, we summed each item to evaluate overall mean differences from baseline to follow-up, with higher scores identifying higher knowledge or confidence. Financial hardship related to cancer was assessed by the COmprehensive Score for financial Toxicity (COST) which consists 11 items that cover worries about out-of-pocket costs, with lower scores indicating greater toxicity.

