2.2 Statistical Analysis Population

The analysis populations include all participants who completed both the baseline and the follow-up survey. For the acceptability analysis individuals must have also complete the interview at study close.

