2.4.2 Missing data

Missing demographic information was supplemented using participant medical records.

For efficacy analyses, individuals missing any of the questions used to calculate the associated sums of questions were dropped from analysis.

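### The SAP 2.3.5 efficacy regressions leave out the baseline score, which may cost precision on the secondary outcomes; the stratified models beside them need relabelling and the protocol's interaction terms.

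*SAP*

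**What the plan says.** SAP 2.3.5 plans three things for each efficacy outcome: a t-test on change between arms, a multivariable linear regression, and stratified regressions. For the regression: "We will control for facility, age at diagnosis, insurance type at diagnosis and gender while examining if treatment group is significantly different". For the stratified models: "We will run multivariable linear models stratified by age at diagnosis and insurance type to examine possible confounding". The baseline score is not a listed covariate, and no other SAP section adds it.

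The score is always available. SAP 2.2: "The analysis populations include all participants who completed both the baseline and the follow-up survey". SAP 2.4.2 adds that "individuals missing any of the questions used to calculate the associated sums of questions were dropped from analysis".

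SAP 2.3.5 does not name the regression's dependent variable, but other sections point to change. SAP 1.3: "Differences in baseline and follow up response values for health insurance literacy and financial toxicity will be used to measure efficacy". SAP 2.1.2 says that "this study is interested in examining the change between the two timepoints". SAP 1.4 powers the study on "differences in the mean improvement in the COST score between the intervention and control groups".

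Protocol 9.1 would adjust only for covariates found to be imbalanced at baseline. It also plans tests for differences in effect by age and interaction tests with treatment arm, and Protocol 5.5 counts age and health insurance status among the moderators. SAP section 3 says the protocol plan was followed and presents the regressions as a check on covariate influence.

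**The concern.** In a randomised comparison of a score measured before and after, the baseline score is usually the strongest available predictor of the outcome. Here the regression adjusts for four other characteristics and omits that one. The protocol's imbalance rule would admit it only after someone had looked at the data. If the correlation between surveys is moderate, the adjusted efficacy estimates will have wider confidence intervals than the collected data allow.

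The lesser matter is the stratified models. They are labelled a confounding check, but no comparison with the crude or pooled estimate is stated. Separate results for two age groups, without an interaction term, are easily read as showing that the programme works in one age group only.

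**Working it through.** **Inputs.** From SAP 1.4: 72 completers (36 per arm), 0.67 SD, 80% power. From Protocol 9.1: COST SDs of 10.11 (younger) and 10.81 (older). From Protocol 5.1.1: 40 enrolled per age group. Assumed, because not given: two-sided alpha of 0.05; the baseline to follow-up correlation r (0.3, 0.5, 0.7, 0.9); three facilities; two levels each for age group, insurance type and gender; and that these covariates explain no further variance.

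**The plan's own figure.** Noncentral t, 36 per arm, d = 0.67, 70 df: power 80.05%. The stated power reproduces. The SAP regression without baseline has 72 − 2 − 5 = 65 df and 80.0% power.

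**Equal SDs s at both surveys.** Var(change) = 2(1 − r)s². Baseline-adjusted variance = (1 − r²)s². The ratio is (1 + r)/2.

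*If 0.67 is in SDs of change*, the adjusted effect size is 0.67/√((1 + r)/2), with 64 df. The equivalent N is 72 divided by the ratio.

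| r | variance ratio | power without → with baseline | equivalent N |
|---|---|---|---|
| 0.3 | 0.65 | 80.0% → 93.5% | 111 |
| 0.5 | 0.75 | 80.0% → 89.8% | 96 |
| 0.7 | 0.85 | 80.0% → 85.9% | 85 |
| 0.9 | 0.95 | 80.0% → 81.9% | 76 |

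*If 0.67 is in cross-sectional SDs*, the effect sizes are 0.67/√(2(1 − r)) without baseline and 0.67/√(1 − r²) with it. Power goes from 66% to 84% at r = 0.3, 80% to 90% at 0.5, and 95% to 97.5% at 0.7. At 0.9 both are about 100%.

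**COST in points.** s = √((10.11² + 10.81²)/2) = 10.47. The 95% CI half-width is t × s × √(2(1 − r)) × √(2/36) for change (70 df) and t × s × √(1 − r²) × √(2/36) for the adjusted model (64 df). It falls from 5.8 to 4.7, 4.9 to 4.3, 3.8 to 3.5 and 2.20 to 2.15 points at the four values of r. The documents give no SD for the HILM or ACA-familiarity sums.

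**Unequal SDs.** If the follow-up SD is k times the baseline SD, the ratio is k²(1 − r²)/(1 + k² − 2rk).
- k = 1.2, r = 0.5: 1.08/1.24 = 0.87.
- k = 1.2, r = 0.7: 0.7344/0.76 = 0.97.
- k = 1.4, r = 0.7: 0.9996/1.00, about 1.00. The slope of follow-up on baseline, rk, is then 0.98, so change already makes nearly the best use of baseline.

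**Dependent variable.** Follow-up equals change plus baseline. With baseline in the model, regressing either one gives the same arm coefficient and standard error; only the baseline coefficient shifts, by 1. Adding baseline therefore also settles what 2.3.5 leaves unstated.

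**Stratified models.** At 10% attrition each age group has about 36 completers, or 18 per arm if split evenly. With a true 0.67 SD effect in both groups, each test has p = 49.7% power (34 df). The chance that exactly one is significant is 2p(1 − p) = 50%. With 12 and 24 per arm, the powers are 34.8% and 62.3%, and that chance is 0.348 × 0.377 + 0.652 × 0.623 = 54%.

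**Interaction by age group.** SE = √(4/18) = 0.471 SD. With 68 df the 95% CI half-width is 0.94 SD, and power is 29% for a 0.67 SD difference in effects; 80% power would need 1.34 SD.

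**The case against.** The best counter-case has five parts.

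- **The planned t-test already uses baseline and is valid.** This stands. A reader might infer from the omission that the efficacy comparison is biased or the sample size wrong. Neither follows: randomisation keeps the change comparison unbiased, and the stated power reproduces.
- **The gain is not assured.** This stands. It is tempting to say the estimates will be less precise, but that depends on r, on the ratio of SDs at the two surveys and, for power, on how 0.67 SD is read. The documents settle none of these.
- **The interaction tests are planned.** This stands for the study as a whole. A reader might take SAP 2.3.5 to mean that none exist, but Protocol 9.1 plans them. They are missing from 2.3.5, while SAP section 3 says the protocol was followed.
- **The stratified models could serve a confounding check.** This partly stands. One might say they can show nothing but subgroup effects, yet 2.3.5 also plans the crude t-test and the pooled adjusted model. The aim is not empty in a completers-only set, and insurance type is not a randomisation stratum, since "participants will be stratified by age at cancer diagnosis (17-26; 27-39 years) and treatment site". What is missing is a stated comparison between these estimates.
- **Protocol 9.1 allows patient random effects.** A model of both surveys could bring baseline in as an outcome. That is only a possibility in the protocol and is not carried into the SAP.

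The analysis may also be finished, since SAP 2.3.3, 2.4.2 and 3 use the past tense. That changes the label on the remedy but not its content.

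**Conclusion.** The point holds as a minor improvement to the secondary efficacy analysis. A covariate that every analysed participant has is left out of the planned regression, and the cost is precision only. With equal SDs at both surveys, adjusted variance is 65% to 95% of change-score variance for r from 0.3 to 0.9. With a follow-up SD 1.2 times baseline it is 87% at r = 0.5 and 97% at r = 0.7, and near a slope of 1 there is no gain. Little is risked in that case, because the price is one degree of freedom.

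The stratified models are a matter of labelling and of carrying protocol text over. Their side-by-side p-values would mislead about half the time under a common 0.67 SD effect at 18 per arm. The interaction estimate is itself too imprecise to be more than exploratory. Feasibility and acceptability, the primary outcomes, are not affected.

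**What to change.** In SAP 2.3.5:

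1. Add the baseline score to the regression, keep the four existing covariates, and name change as the dependent variable.
2. Report the adjusted difference with a 95% CI for each efficacy outcome beside the change t-test.
3. Use this fixed covariate set in place of the imbalance rule in Protocol 9.1.
4. Relabel the stratified models as exploratory effect modification. Carry over from Protocol 9.1 the arm-by-age-group and arm-by-insurance interaction terms, with CIs and a note on low power.

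If results are already known, keep the change t-test as the planned comparison and label the baseline-adjusted model post hoc.

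No new data are needed. Against the SAP regression the cost is one residual degree of freedom (65 to 64), about 0.02 percentage point of power or less. Against the t-test (70 df) the full model uses six, about 0.1 percentage point, under the factor levels assumed above.

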2.4 Data Processing Conventions

2.4.1 Definition of baseline

For this study, baseline is defined as the information collected at time of first completed survey of each participant. For instances where a patient started multiple surveys, data from the last survey completed was used.

2.4.2 Missing data

Missing demographic information was supplemented using participant medical records.

For efficacy analyses, individuals missing any of the questions used to calculate the associated sums of questions were dropped from analysis.

2.4.3 Time window

Not applicable

2.4.4 Unscheduled Visits

Not applicable

2.4.5 Center Pooling

Participants were randomized in a manner that required approximately equal enrollment of participants from each site to control for any possible center effects, further we plan on including facility as a variable in our models. As such, no additional controlling for site will be done all participants will be pooled for analyses.

3. Changes to Planned Analysis from The Protocol

The protocol analysis plan was followed; however, we did run multivariable regressions to ensure that covariates did not influence our findings. We also performed sensitivity analyses examining report of policy holder status and by site of recruitment.

4. Interim Analysis

No official interim analyses are planned

5. Statistical Analysis Software

All statistical analysis and summary information will be completed in STATA 14.0 or higher.

6. References

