5.4 Randomization

Aim 2: All participants will be randomized into one of two groups: A or B. Randomization will be stratified by age at cancer diagnosis (17-26; 27-39 years) and treatment site and blocked into groups of 4 patients (2 control, 2 intervention) to ensure that control and intervention groups are approximately balanced by age and within sites. Random allocations within strata will be computer generated and automatically assign individuals to a study arm after the study coordinator determines patients' eligibility and obtains consent.

Aim 3: 20 participants will be randomly invited to participate in an exit interview. Those 20 participants will be equally pulled from the control and intervention group.

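### SAP 2.4.5 wrongly says randomisation required roughly equal enrolment by site, and the plan does not say whether the strata-adjusted model or the unadjusted t-test is the main efficacy comparison

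*SAP*

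**What the plan says.** On pooling, SAP 2.4.5 opens with "Participants were randomized in a manner that required approximately equal enrollment of participants from each site to control for any possible center effects". The same sentence adds a second ground: "further we plan on including facility as a variable in our models". The decision follows: "As such, no additional controlling for site will be done all participants will be pooled for analyses".

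On the design itself, Protocol 5.4 says "Randomization will be stratified by age at cancer diagnosis (17-26; 27-39 years) and treatment site and blocked into groups of 4 patients", two per arm in each block. It gives the purpose as "to ensure that control and intervention groups are approximately balanced by age and within sites". SAP 1.1 describes the same scheme and purpose. Protocol 5.1.1 sets enrolment targets by arm (40 and 40) and by age group (40 and 40), and none by site.

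On the efficacy analysis, SAP 2.3.5 first says "Differences in these change values by group will be examined using sample t-tests". It then plans a linear regression for each efficacy outcome with facility, age at diagnosis, insurance type and gender as covariates. The baseline score is not listed. For satisfaction, SAP 2.3.4 plans only the t-test on change.

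**The concern.** Two things are wrong or left open.

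First, 2.4.5 describes a property that the design does not have. Stratified blocking makes the arms similar in size within each stratum; how many patients a site contributes depends on referral. Equal site sizes would not by themselves control centre effects either. The sentence conflicts with SAP 1.1 and Protocol 5.4, and could be carried into the trial report.

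Second, the t-tests omit the factors used to randomise. If those factors predict the outcome, stratified allocation removes their contribution from the chance difference between arms, but the t-test's standard error still includes it. The p-value is then too large and power is lost. The regressions correct this for efficacy, but the plan does not rank the two analyses, so two competing comparisons exist for each outcome. Nothing corrects it for satisfaction.

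**Working it through.** **1. What the scheme constrains.** An incomplete block of four can leave a stratum out of balance by at most 2. With two age strata per site, the arms within a site can differ by at most 2 + 2 = 4 at randomisation. Nothing limits the site total. A simulation of 80 patients at three sites (the three named in Protocol 3.1; 4,000 trials per case; referral mixes assumed) gave:

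| Assumed site mix | Mean site sizes | Largest arm difference within a site |
|---|---|---|
| 33/33/33% | about 27/27/27 | 4 |
| 60/30/10% | 48/24/8 | 4 |
| 80/15/5% | 64/12/4 | 4 |

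Site size follows the referral mix; arm balance within site holds throughout.

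**2. The plan's own power figure.** Inputs from SAP 1.4 and Protocol 9.1: 0.67 SD difference in mean COST improvement, 72 completers, hence 36 per arm at 1:1. Alpha and sidedness are not stated; I assume two-sided 0.05. The noncentrality is 0.67 × √(36/2) = 2.843. The normal approximation gives Φ(2.843 − 1.960) = 81.1%; the noncentral t with 70 df gives 80.05%. The stated power of at least 80% reproduces, and it is for an unstratified two-sample test.

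**3. Effect of adjusting for the strata.** If the strata explain a share R² of the variance in change, the residual SD is √(1 − R²), and the effect in residual SDs is 0.67/√(1 − R²). The formula column puts this into the same noncentral t calculation with 70 df. The other columns come from a simulation of 6,000 trials per cell: 80 randomised in blocks of four within 3 sites × 2 age groups, 60/30/10 site mix, and 72 completers drawn at random. The model is linear with arm, site and age group.

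| R² (assumed) | Effect, residual SDs | Adjusted power, formula | Power, t-test (sim.) | Power, model (sim.) | Type I, t-test (sim.) | Type I, model (sim.) |
|---|---|---|---|---|---|---|
| 0 | 0.670 | 80.1% | 80.5% | 79.9% | 4.9% | 4.8% |
| 0.10 | 0.706 | 84.0% | 81.5% | 83.4% | 4.5% | 5.3% |
| 0.20 | 0.749 | 88.0% | 81.4% | 87.4% | 3.0% | 5.0% |
| 0.30 | 0.801 | 91.8% | 82.3% | 91.0% | 2.6% | 5.2% |

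Monte Carlo error is about 0.3 points for type I error and 0.5 points for power.

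**4. Whether the documents fix R².** Protocol 9.1 gives COST at enrolment in the navigation program as 25.79 (SD 10.11) for younger and 18.22 (SD 10.81) for older AYAs. With equal groups, the between-group variance is ((25.79 − 18.22)/2)² = 14.33 and the within-group variance is (10.11² + 10.81²)/2 = 109.53, so R² = 14.33/(14.33 + 109.53) = 0.116. That is for the COST level. The endpoint is change. If the age gap stays constant over time, age explains none of the variance in change, and the gain from adjusting for age is zero. The documents give no R² for change and none for site, so step 3 has to be read as a range starting at 0.

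**The case against.** The strongest reply is that the efficacy analysis already handles the strata. The word additional in 2.4.5 follows both grounds, so it means beyond facility adjustment. The 2.3.5 regressions include both stratification factors for every efficacy outcome, models stratified by age at diagnosis are planned, and SAP section 3 reports a sensitivity analysis by site. The randomisation is described correctly elsewhere. All of this stands. A reader might infer from 2.4.5 that pooling rests only on the equal-enrolment statement, or that site and age are never adjusted for; the documents do not support either reading.

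A reader might also take the t-tests to be the declared headline analysis. No document says so. It is an inference from three places: Protocol 9.1 names independent-sample t-tests for the between-group comparison, the sample size uses an unstratified test, and SAP section 3 presents the regressions as a check on the findings. What remains is that the main comparison is not named.

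The consequence is also mild. The t-test keeps the power of at least 80% that the plan claims, its error is on the conservative side, and efficacy is secondary. That limits the severity, but leaves the wording error, the unranked analyses, the missing baseline score and the unadjusted satisfaction test in place.

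**Conclusion.** The statement in 2.4.5 is incorrect and should be changed whatever the outcome data look like. Beyond that, the gap is one of specification: the main between-arm efficacy comparison is not named, the planned regression leaves out the baseline score, and satisfaction has no analysis that respects the stratification.

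The cost of relying on the t-test runs from nothing, if the strata explain none of the change, to roughly 9 points of power at R² 0.30 (91.0% − 82.3% = 8.7 in simulation). This rests on two-sided alpha 0.05, 36 completers per arm, three sites and an assumed 60/30/10 site mix. It would be wrong to infer inflated false positives: the simulated type I error of the t-test is at or below 5% throughout. It would also be wrong to read the 0.116 for COST level as the loss for the change endpoint. The gain from adding the baseline score is not quantified, because the documents give no correlation between baseline and follow-up. Severity: minor.

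**What to change.** 1. In SAP 2.4.5, replace the sentence on equal enrolment with: *Randomisation was stratified by site and age at diagnosis, which balances arms within strata; facility is included in the models.*
2. In SAP 2.3.5, name the linear model with arm, facility, age stratum and baseline score as the main between-arm analysis, and keep the t-test as supportive. The planned insurance-type and gender terms may stay.
3. In SAP 2.3.4, compare satisfaction between arms in a model with arm, facility and age stratum. Add a baseline score only if one exists: SAP 1.3 places these questions in the follow-up survey, while 2.3.4 speaks of change between time points.

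The cost is small but not nil. This is not exactly the model now in 2.3.5, and none is planned for satisfaction. With three sites and 72 completers, residual degrees of freedom fall from 70 for the t-test to 72 − 6 = 66 with arm, two facility terms, age stratum and baseline score, and somewhat further with insurance type and gender. At R² 0 there is no gain from the strata. SAP section 3 is written in the past tense and reports regressions already run. If results have been seen, the change must be dated and labelled post hoc, and both analyses reported.
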